COMIRB Protocol
COLORADO MULTIPLE INSTITUTIONAL REVIEW BOARD
[name] [contact] [contact]-
[name]

Protocol #: COMIRB 15-0036

**Project Title: Use of Ultrasonic Bone Scalpel in Adolescent Idiopathic Scoliosis – Randomized
Clinical Trial**

Principal Investigator: [name]

Version Date: 7/6/2015

I. Hypotheses and Specific Aims:

The primary purpose of this randomized trial is to compare the efficacy of an ultrasonic bone scalpel (or osteotome device) with standard of care surgical instruments during posterior spine fusion with instrumentation. The primary outcome variable in this trial is estimated blood loss per spine level fused (EBL/level). Secondary outcome variables include the probability of meeting the intraoperative blood transfusion criteria, incidence of adverse events, and incidence of surgical site infections. Subjects with adolescent idiopathic scoliosis undergoing planned posterior spinal fusion with instrumentation will be recruited from a single tertiary recruitment center for this trial.

Primary Aim 1: Compare estimated blood loss per level fused

Hypothesis 1: The average estimated blood loss per level fused will be significantly lower in the ultrasonic bone scalpel (USBS) group compared to the standard of care group.

Secondary Aim 1: Compare the incidence of adverse events in the two groups.

Hypothesis 2: There will be no difference in the incidence of adverse events in the bone scalpel group compared to the standard of care group.

Secondary Aims 2-3: Compare the proportion of patients meeting intra-operative blood transfusion criteria in the two groups.

Hypothesis 3: The proportion of subjects meeting the intra-operative blood transfusion criteria will be significantly lower in the bone scalpel group compared to the standard of care group.

II. Background and Significance:

Adolescent idiopathic scoliosis (AIS) is a common spine deformity in children. In severe cases posterior spinal fusion surgery (PSF) is indicated to correct the deformity and prevent curve progression. Due to the duration and invasiveness of this procedure, PSF is associated with high intraoperative blood loss. On average, AIS patients typically lose 65-150 mL per vertebral level during spinal fusion surgery.[1] With regard to total blood volume, AIS patients typically lose 25-30% of their total blood volume during PSF.[1, 2] The percent of patients who receive an

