intraoperative transfusion during PSF surgery is variable, but has been reported as low as 20-30% and as high as 50-75%.[2-6] The amount transfused also widely varies and ranges from 1-8 units of red blood cells.[2, 7] Minimizing intraoperative blood loss (EBL) is of great importance due to the association between increased blood loss and increased risk of postoperative complications.[8-10]

The utilization of an FDA approved ultrasonic bone scalpel (USBS) may help decrease EBL during PSF. The Misonix BoneScalpel® is a device that utilizes ultrasonic frequencies to “cut” through osseous structures. At the tip of the device is a blunt blade that vibrates longitudinally at a frequency of 22,500 times per second. This blunt, vibrating blade is selective between osseous tissue and softer, connective tissue. Further, the tip is irrigated by a sterile saline solution which helps to provide cooling and reduce the risk for thermal injury.[11, 12] This device has been used for various procedures in various specialties. It has been used in maxillofacial surgery in order to perform a more precise and controlled osteotomy.[13, 14] It has also been used in tumor resection and when performing surgery close to the spinal cord.[12, 15-18]

The literature surrounding the use of the USBS in pediatric spine surgery is more limited. Several retrospective studies cite the USBS as safe and effective for various procedures such as spinal decompression, posterior releases, posterior facetectomies, posterior osteotomies, and laminectomies.[16, 19-21] Bydon et al. (2014) reported that patients treated with the USBS showed a trend toward decreased complications. Bartley et al. (2014) observed a statistically significant difference in EBL between groups. Blood loss in the USBS group was 30-40% less than blood loss in the historical control group. The majority of studies involving pediatric spine surgery are retrospective in nature. The lack of randomization creates concern about potential for selection and/or indication bias. Therefore, the purpose of this randomized trial is to compare the safety and efficacy of the USBS relative to standard of care instruments in a pediatric population undergoing PSF.

III. Preliminary Studies/Progress Report:

No preliminary studies have been performed at this institution. Please see the above section for studies performed at other institutions.

IV. Research Methods not only

a. Outcome Measure(s):

Primary Clinical Outcome

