Estimated blood loss/level [^]
Secondary Clinical Outcomes
Intraoperative and postoperative complications (events that cause a deviation from routine care) ^{^†‡}
Probability of meeting blood transfusion criteria (see section) ^{^†}
Procedure Time (first incision to close) [^]

Demographics/Covariates (potential confounding variables)	
Age at surgery*	BMI percentile at surgery*
Gender at surgery*	Weight (kg) at surgery*
Exposure to second hand smoke*	Preoperative Lenke Classification*
Preoperative major Cobb angle*	Preoperative hemoglobin/hematocrit*
Postoperative major Cobb angle††	Postoperative hemoglobin/hematocrit†
Intraoperative use of intrathecal narcotics^	Donor hematocrit^
Vertebral levels fused^	Intraoperative use of antifibrinolytic^

Exploratory Variables	
Unplanned return to OR††	Surgical site infection†
Procedure Time^	

* Collected preoperatively or day of surgery (before surgery)

^ Collected intraoperatively

† Collected postoperatively: short term follow-up, during initial hospital stay

‡ Collected postoperatively: long term follow-up, one year postoperative

I. Description of Population to be Enrolled:

All patients with a diagnosis of Adolescent Idiopathic Scoliosis who are scheduled for spinal fusion surgery and meet the following criteria will be eligible to participate in the study:

Inclusion Criteria:

1. 10-18 years of age
2. Diagnosis of AIS
3. Scheduled for a posterior spinal fusion (without Schwab Grade II or higher osteotomy)

Exclusion Criteria:

1. Plan for a posterior column osteotomy of Schwab Grade II or higher
2. Prior spinal surgery
3. MRI abnormalities (such as syrinx and/or chiari malformations)
4. Subjects with medical comorbidities (e.g. heart, lung, kidney disease)
5. Subjects with bleeding diatheses
6. Non-idiopathic etiology for scoliosis

II. Study Design and Research Methods

a. Power Analysis

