The purpose of this single blinded, randomized, controlled, superiority trial is to compare the efficacy of an ultrasonic bone scalpel with standard of care surgical instruments during posterior spine fusion with instrumentation. The primary aim of this study is to compare differences in estimated blood loss per fusion level (EBL/level) between groups ($\theta = \theta_{standard\ care} - \theta_{USBS}$). We aim to test the null hypothesis that the difference between groups is less than or equal to 0 ($H_0: \theta \leq 0$). Based on a previous retrospective cohort study in a similar target population[21], we anticipate the EBL/level in the proposed study will be 48 mL/level (± 30) in the USBS group (θ_{USBS}) and 72 mL/level (± 28) in the standard instrument group ($\theta_{standard\ care}$). Although there are no universally established thresholds for defining a clinically meaningful difference in

EBL/level, the investigators are confident that the 33% reduction in blood loss per level observed in the previous study is representative of a clinically meaningful reduction in blood loss ($H_+ \theta \geq 24$ or $H_+ \theta \geq 33\%$). Based on a symmetric two sided, two stage group sequential design with O'Brien-Fleming stopping criteria and an alpha level of 0.05, we determined that a sample size of 62 subjects (31 subjects per group) would provide 90% power to reject the null hypothesis of no difference between groups (See Trial Monitoring section for information about the stopping criteria). This estimate assumes a group difference of 24 mL/level and a standard deviation of ± 28 in the standard instrument group and a standard deviation of ± 30 in the USBS group. Assuming a dropout rate of approximately 15%, we intend to enroll 36 subjects per group to achieve the desired statistical power. The estimated dropout rate is based on previous studies in a similar patient population, adolescents with idiopathic scoliosis.

b. Subject Screening:

All surgical patients under the care of two high volume pediatric orthopedic surgeons will be screened for study eligibility. All patients who elect to undergo spinal surgery at Children's Hospital Colorado under the care of the investigators of this study will be screened for study eligibility by the research coordinator (research assistant). Patients who are determined to meet the inclusion and exclusion criteria from above will be approached by the study team.

c. Enrollment and Consent:

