An intent to treat analysis of all randomized subjects will be performed. Descriptive statistics will be used to compare the distribution of demographics and clinical characteristics in the two groups. Baseline covariates significantly different between groups will be considered as potential confounding variables in subsequent statistical models. The primary aim of this study is to compare differences in estimated blood loss per fusion level (EBL/level) between the USBS and standard of care groups ($\theta = \theta_{USBS} - \theta_{standard\ care}$). We aim to test the null hypothesis that the difference between groups is less than or equal to 0 ($H_0: \theta \geq 0$). An independent sample t-test or multiple variable linear regression analysis, as appropriate, will be used to compare total EBL/level in the two study groups. For the secondary outcome variables, Chi-square tests will be used to compare differences in the categorical variables (the risk of adverse events, proportion of subjects meeting the intra-operative blood transfusion criteria) between the groups. Independent sample t-tests or Wilcoxon rank sum tests will be used to compare differences in the continuous variables (operative time, post-operative length of stay, and intraoperative irrigation volume).

e. Trial Monitoring/Human Subjects Research Consideration

Data Safety and Quality - All data will be collected and stored in a REDCap database. Access to the database will be restricted to investigators involved the study protocol per study personnel section of the COMIRB protocol application and/or the study delegation of duties log. Photographs obtained during surgery will be de-identified, assigned an appropriate study ID and will be stored on a secure departmental server that is managed by the IT department at Children's Hospital Colorado. The study coordinators will review data stored in the REDCap database on an ongoing basis. Potential outliers and/or biologically implausible data points will be identified and reviewed on an individual basis with the Principal Investigator.

Safety Monitoring – Based on the advice of our clinical trial study design consultant, [name], a Data Safety Monitoring Board (DSMB) will review the safety and efficacy of the study. The DMSB will consist of an orthopaedic surgeon not directly

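### Hypothesis 2 predicts no difference in adverse events, but the only planned analysis is a chi-square test of difference, which cannot support that prediction in a trial sized for blood loss alone

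*Combined protocol and SAP*

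**What the plan says.** Hypothesis 2, under Hypotheses and Specific Aims, reads: "There will be no difference in the incidence of adverse events in the bone scalpel group compared to the standard of care group". The aim it serves is neutral and asks only for a comparison of incidence between the groups.

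Background and Significance closes by making safety part of the reason for the trial: "the purpose of this randomized trial is to compare the safety and efficacy of the USBS relative to standard of care instruments". The endpoint is listed under Outcome Measure(s) as "Intraoperative and postoperative complications (events that cause a deviation from routine care", collected during surgery, during the hospital stay and up to one year.

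The Data Analysis Plan gives one between-group analysis for it: "Chi-square tests will be used to compare differences in the categorical variables (the risk of adverse events" and, in the same parenthesis, the proportion meeting the transfusion criteria. The analysis set is all randomized subjects.

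The Power Analysis describes a "The purpose of this single blinded, randomized, controlled, superiority trial" and sizes it on blood loss per level only, at 31 per group with 36 per group to be enrolled. No expected rate, power, margin or confidence interval is given for adverse events. The confidence intervals in the Decision/Stopping Criteria table all concern blood loss per level.

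**The concern.** Hypotheses 1 and 3 are worded so that a significant test in the predicted direction supports them. Hypothesis 2 runs the other way: its prediction is the null of its own test. A chi-square test can contradict that prediction. It cannot support it, because a large p-value may mean similar risks or too few patients, and the smaller the trial, the easier a large p-value becomes.

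What is at stake is the safety sentence in the final report. If Hypothesis 2 is answered with the planned test alone, a non-significant result is the only outcome that can look like confirmation, and nothing in the plan tells the reader how large an excess risk remains possible.

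**Working it through.** **Inputs from the documents.** 31 per group evaluable and 36 per group enrolled (Power Analysis); about 16 per group if the trial stops at Stage 1 (Decision/Stopping Criteria); alpha 0.05, stated for the primary outcome and assumed here for adverse events, two-sided. 

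**Assumed inputs.** Adverse event rates, because no overall rate is given. Standard-group rates from 5% to 30% are shown.

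**1. The plan's own sample size.** Mean variance = (28² + 30²)/2 = 842. Fixed-design n per group = 2 × 842 × (1.9600 + 1.2816)² / 24² = 30.7, so 31. With the stated bounds 2.7965 and 1.9774, the two-stage design has 90.1% power at 31 per group. The figure reproduces, but it concerns blood loss per level and says nothing about adverse events.

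**2. Chance that the chi-square test misses a true increase.** For event counts x₁ and x₂ in n per group, let p̄ = (x₁ + x₂)/2n and z = (|x₁ − x₂|/n) / √(2p̄(1 − p̄)/n). The uncorrected test rejects when z > 1.96. Power is the sum of Bin(x₁; n, p₁) × Bin(x₂; n, p₂) over all rejecting pairs, and the miss probability is 1 − power.

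| Assumed rates | Power, n = 31 | Miss, n = 31 | Miss, n = 36 | Miss, n = 16 |
|---|---|---|---|---|
| 5% v 10% | 0.110 | 0.89 | 0.87 | 0.97 |
| 10% v 20% | 0.199 | 0.80 | 0.78 | 0.89 |
| 20% v 40% | 0.408 | 0.59 | 0.53 | 0.75 |
| 30% v 60% | 0.689 | 0.31 | 0.27 | 0.59 |
| 5% v 15% | 0.273 | 0.73 | 0.68 | 0.90 |
| 10% v 30% | 0.516 | 0.48 | 0.42 | 0.70 |
| 15% v 45% | 0.755 | 0.25 | 0.18 | 0.51 |
| 20% v 60% | 0.918 | 0.08 | 0.05 | 0.33 |

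The last column is not remote. At a true blood-loss difference of 24 mL/level, the Stage 1 statistic has mean 24/√((28² + 30²)/16) = 2.34, so the chance of stopping there for benefit is 1 − Φ(2.7965 − 2.34) ≈ 0.32.

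As one anchor from the protocol's own dural tear table, the 337-patient study lists 5.7% with USBS and 3.6% without. At those rates power is about 0.04 with 31 per group.

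**3. What an interval would show.** Newcombe's interval combines the Wilson limits (l, u) of each group. With d = p₁ − p₂, the lower limit is d − √((p₁ − l₁)² + (u₂ − p₂)²) and the upper limit is d + √((u₁ − p₁)² + (p₂ − l₂)²).

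- 2/31 v 2/31: Wilson limits 0.018 to 0.207 around 0.065 in each group. d = 0, half-width √(0.0466² + 0.1427²) = 0.150, so −15 to +15 points.
- 7/31 v 3/31: d = 0.129. Lower 0.129 − √(0.1118² + 0.1522²) = −0.060; upper 0.129 + √(0.1723² + 0.0633²) = 0.313. So −6 to +31 points, with chi-square p = 0.167.
- 9/31 v 3/31, an observed threefold excess: −1 to +38 points, with p = 0.054.

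Identical counts therefore leave an excess of up to 15 points open, and an observed tripling can be non-significant.

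**4. Sparse counts.** An expected cell falls below 5 when 31 × p̄ < 5, that is when the pooled rate is under about 16%. At such rates the chi-square approximation is itself doubtful.

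**The case against.** A reader might infer that the protocol lays down a rule under which p > 0.05 means equal safety. It does not. Hypothesis 2 is an expectation, its aim is a neutral comparison, and the only written decision rules concern blood loss per level. The closing summary of knowledge to be gained speaks of possible advantages and disadvantages and claims no proof of equal safety. This objection stands: the risk lies in how a result could be read, because the plan offers nothing else to read it by.

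A reader might also take the miss rates at low baselines as a general result. They are not. The endpoint is broad and runs to one year, so a high event rate is possible. At 20% v 60% the test misses only 8% of the time. The full range is needed because the documents do not say where in it the trial lies.

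Three further points carry some weight. Efficacy is the stated primary purpose, and low power for a secondary safety outcome is usual at this size and is not in itself an error. The plan also says "An intent to treat analysis of all randomized subjects will be performed", so up to 36 per group may contribute, especially for intraoperative and in-hospital events; the table shows that this changes little. Finally, a DSMB reviews safety, and all adverse events go to it and to the ethics board. That protects patients during the trial and confines the issue to reporting, but it does not govern what is concluded about Hypothesis 2.

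**Conclusion.** The concern holds in a limited form. Hypothesis 2 is the null of its only planned analysis, and the plan has no margin, interval or other limit on the safety conclusion, so a non-significant result could be taken as support that it cannot provide. With 31 per group, the probability of missing a doubling or tripling of risk runs from 0.08 to 0.89 across the assumed rates. For standard-group rates of 10% or less it is at least 0.48. These figures rest on assumed event rates, an uncorrected two-sided test at 0.05, and 31 evaluable patients per group. The documents do not support the stronger claim that the plan equates non-significance with safety. The matter merits correction because safety is a named purpose and the remedy needs no more patients.

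**What to change.** Restate Secondary Aim 1 and Hypothesis 2 as estimation of the difference in adverse event risk between the groups. In the Data Analysis Plan, add the risk difference (USBS minus standard) with a two-sided 95% score-type interval, for example Newcombe's. State that the safety conclusion will rest on the excess risk that this interval excludes, and not on a non-significant chi-square test. The choice among score-type methods is secondary; having an interval is what matters.

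The cost is about two sentences and one extra interval, with no added patients, visits or data. The downside is a weaker, but correct, safety statement.

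A formal non-inferiority test is not a realistic substitute at this size. At an assumed rate of 10% in both groups, a margin of 10 points, one-sided 0.025 and 80% power, it needs (1.960 + 0.842)² × 2 × 0.10 × 0.90 / 0.10² ≈ 141.3, so 142 per group. The rate and margin are illustrations, since the documents give neither.

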Patients will be randomized 1:1 into two different treatment groups using a block randomization scheme. Using the Proc Plan procedure within SAS 9.4 (SAS Institute, Carey NC), blocks will be constructed based on surgeon and patient gender. Each surgeon will have a randomization list generated, and patient assignment will be made after the informed consent process has been performed to the next assignment on the list. Randomization assignments will not be revealed to the study personnel until after the patient has been enrolled in the study so as not to unduly bias the consent process.

Blinded evaluators will be used to calculate the primary outcome variable of interest, estimated blood loss per level fused. All other study personnel, including the surgeons, will not be blinded to participant treatment assignment which is necessary to ensure the correct protocol is followed. Patients and their families will be blinded to study assignment to minimize the risk of assignment related study withdrawal. Patients and their families will not have the assignment revealed to them after the surgery as it will not affect their plan of care. If desired, treatment allocation may be revealed at the final study visit at one year following surgery.

e. Intraoperative Estimated Blood Loss

Estimated blood loss will be determined by 3 different methods. The first and primary method is to use the estimated blood loss listed on the cell saver report. This measurement is generated by the cell saver based on the blood collected. The other two methods determine blood loss through a calculation.

Method 2:

With this method, the EBL measurements will be based on the contents of the blood and fluid collection canisters as well as the volume reports generated by the cell saver system. To ensure blinding, final levels of fluid bags and canisters will be photographed by the study surgeon immediately after the procedure is complete. Photographs will be taken by the camera features from an iPhone 6. Photographs will be taken at a distance of two feet from the canisters and bags and such that the meniscus of the fluid is at eye-level with the lens. Photographs will be reviewed by blinded evaluators at two intervals, prior to the interim analysis and following final enrollment. Two blinded evaluators will be used for each measurement, and their measurements will be averaged for use in the final calculation.

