EBL will be calculated in the following manner: First, the total fluid volume will be calculated: The volume of the contents of all of the blood and fluid canisters used during the course of the surgical procedure will be recorded based on the photographs. To this we will add the cell saver intake fluid, taken from a report generated by the cell saver system. Next, the total irrigation volume used during surgery will be calculated. The irrigation volume will be estimated as the difference in volume of the irrigation bag at surgery cut versus surgery close. For subjects in the USBS group, the total irrigation volume will also include the difference in volume of the USBS irrigation bag at surgery cut versus surgery close. Estimated blood volume will be calculated as total fluid volume minus irrigation volume.

Method 3:

To validate the above described method 2, the study personnel will also use the same method of calculated blood loss as was used in a study by Da Cunha et al (2015).[22] The blood loss calculation from this study was adapted from the method proposed in Brechter et al (1997).[23] This method calculates blood loss through the following mathematical model:

$$EBL = [EBV * (Hb_{pre} - Hb_{post}) / Hb_{pre}] + [Donor RBC_{normalized}] + [Cell Salvage RBC_{normalized}]$$

Where:

EBV = Estimated Blood Volume = Patient Weight (kg) x 70 ml/kg

Hb_{pre} = preoperative patient Hemoglobin

Hb_{post} = postoperative Day One Patient Hemoglobin

Donor RBC_{normalized} = [donor RBC volume] x [(donor Hct) / (Hct_{pre} + Hct_{post}) / 2]

Cell Salvage RBC_{normalized} = [cell saver RBC volume] x [(cell saver Hct) / (Hct_{pre} + Hct_{post}) / 2]

Hct_{pre} = Preoperative Patient Hematocrit

Hct_{post} = Postoperative Patient Hematocrit

Patient's weight will be measured the day of surgery. Hct_{pre} and Hb_{pre} will be taken by the lead anesthesiologist prior to first incision through an ISTAT. Hct_{post} and Hb_{post} will be taken 12-18 hours after the end of the procedure through an ISTAT. Donor and cell saver Hct will be taken by the lead hematologist before bags are sent up to the OR.

f. Intraoperative Transfusion Guidelines

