Study data will be collected and managed using REDCap (Research Electronic Data Capture). REDCap is a secure web application designed to support data capture for research studies, providing user-friendly web-based case report forms, real-time data entry validation (e.g. for data types and range checks), audit trails and a de-identified data export mechanism to common statistical packages (SPSS, SAS, Stata, R/S-Plus). The system was developed by a multi-institutional consortium which includes University of Colorado–Denver and was initiated at Vanderbilt University. The database is hosted at the University of Colorado–Denver Development and Informatics Service Center (DISC), which will be used as a central location for data processing and management. REDCap data collection projects rely on a thorough study-specific data dictionary defined in an iterative self-documenting process by all members of the research team with planning assistance from the DISC. This iterative development and testing process results in a well-planned data collection strategy for individual studies. REDCap also includes a powerful tool for building and managing online surveys. The research team can create and design surveys in a web browser and engage potential respondents using a variety of notification methods. REDCap is flexible enough to be used for a variety of types of research and provides an intuitive user interface for database and survey design and data entry.

c. Potential Scientific Problems:

One potential scientific problem in this study has to do with the quantification of estimated blood loss. Past literature has revealed this measurement to be variable.[2, 25] We hope to overcome this problem by strictly adhering to the EBL collection protocol outlined above. Two research coordinators will take measurements and their measurements will be averaged for a final EBL. In this way, although the measurement is prone to misclassification, we anticipate misclassification to be non-differential. A calculated blood loss will be performed to attempt to find reproducibility between the two types of measurements and reduce potential bias. Furthermore, the research assistants, who will be performing EBL measurements and calculations, will be blinded.

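### The primary blood-loss value is described in two unreconciled ways, and the blinding claimed for EBL calculations cannot hold for Method 2 as written

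*Combined protocol and SAP*

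**What the plan says.** Section numbers here are those nested under section IV, Research Methods, of the combined protocol and SAP.

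- **II.e, Intraoperative Estimated Blood Loss**, lists three methods and ranks them: "The first and primary method is to use the estimated blood loss listed on the cell saver report". Of that value it says "This measurement is generated by the cell saver based on the blood collected". Methods 2 and 3 are introduced as the calculated ones.
- **II.e, Method 2**, works from photographs of canisters and fluid bags: "Two blinded evaluators will be used for each measurement, and their measurements will be averaged for use in the final calculation". Irrigation is then subtracted. In the USBS arm only, the irrigation total also includes the change in the device's own irrigation bag.
- **II.e, Method 3**, is a hemoglobin-based formula with a stated purpose: "To validate the above described method 2, the study personnel will also use the same method of calculated blood loss".
- **II.d, Randomization and Blinding**: "Blinded evaluators will be used to calculate the primary outcome variable of interest, estimated blood loss per level fused".
- **III.c, Potential Scientific Problems**, discusses variability in EBL and appeals to strict adherence to the collection protocol already set out. It continues: "Two research coordinators will take measurements and their measurements will be averaged for a final EBL". It then argues that "although the measurement is prone to misclassification, we anticipate misclassification to be non-differential", and adds that "the research assistants, who will be performing EBL measurements and calculations, will be blinded".
- **III.d (analysis plan) and III.e (monitoring dataset and stopping criteria)** refer to blood loss per level without restating its source.

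**The concern.** EBL per level is the only quantity compared with the efficacy boundaries at the interim and final analyses. Its source should therefore read the same way wherever the protocol describes it. Here one section makes a machine-reported number primary, while another describes the final number as an average over two people.

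Two things are at stake. First, the protocol's only argument that measurement error is unrelated to treatment is made for the averaged measurement, not for the value labelled primary. Second, the surgeons and other study personnel are unblinded, so protection against assessment bias rests on the blinded evaluators. If those evaluators also do the Method 2 calculation, as III.c implies, they learn the arm in doing it.

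**Working it through.** **1. Which method does III.c describe?**

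| Source | How the value arises (II.e) | Two readings to average? | Fits the final EBL in III.c? |
|---|---|---|---|
| Method 1, named primary | Taken from the cell-saver report | No | No |
| Method 2 | Two evaluators read volumes from photographs; irrigation is subtracted | Yes | Yes |
| Method 3 | Weight, pre- and postoperative hemoglobin and hematocrit, donor and salvaged red cells | No | No |

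Only Method 2 fits. III.c also speaks of two types of measurement where II.e has three, and it never mentions the cell-saver EBL. Two further details point the same way without proving it: the photographs are read before the interim analysis and after final enrollment, matching the two looks, and Method 3 is there to validate Method 2 rather than Method 1.

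**2. Can the Method 2 calculation be done blind?** From II.e:

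- Blood loss = (canister volumes + cell-saver intake) − irrigation volume.
- Standard arm: irrigation volume = change in the irrigation bag.
- USBS arm: irrigation volume = change in the irrigation bag + change in the USBS irrigation bag.

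The formula has an extra term in one arm. Whoever applies it must know whether a USBS bag was used, which is the allocation. Reading a volume from a photograph need not reveal the arm; completing the calculation does. III.c assigns both tasks to the blinded assistants.

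**3. Do the plan's boundaries depend on this?** Inputs: SDs of 28 and 30 mL/level (Power Analysis); |Z| limits of 2.7965 and 1.9774, and 31 per group at the end (stopping criteria).

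- Final: SE = √((28² + 30²)/31) = √(1684/31) = 7.37; 1.9774 × 7.37 = 14.57 mL/level (plan: 14.6).
- Interim at 50% information, 15.5 per group: SE = √(1684/15.5) = 10.42; 2.7965 × 10.42 = 29.15 mL/level (plan: 29.2).
- Under the same two-stage design, power at 24 mL/level is 0.9006 (plan: 90%) and type I error is 0.0250 per side (plan: 0.025).

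The design figures reproduce. The Z limits apply to whichever EBL source is analysed. The mL/level cut-offs and the power also rest on the two SDs, and the documents do not say which measurement method those SDs describe. No method-specific SD, bias or between-method disagreement is given, so no consequence for power or error can be calculated.

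**The case against.** The strongest reply is that the endpoint is already defined. II.e is the operative measurement section and plainly calls the cell-saver EBL primary. A plan need not repeat the source of a defined endpoint each time it names it, so silence in III.d and III.e is not in itself ambiguity. III.c is a discussion of limitations; it defers to the earlier collection protocol and can be read as quality control for Method 2. The II.d statement that blinded evaluators calculate EBL per level is compatible with Method 1, because a reported EBL must still be divided by levels fused.

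All of this stands, and it rules out saying that the plan has no primary source. It does not make III.c correct. That section is offered as the answer to measurement error in EBL generally, yet describes one non-primary method. On the harmonised reading, its misclassification argument does not cover the primary endpoint; on the literal reading, it contradicts II.e. Either way the text needs an edit.

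On blinding, the Method 2 text alone could be read as having evaluators supply readings and someone else finish the calculation. III.c closes off that reading by giving the blinded assistants the calculations too. A reader might also infer that the photographs are uncoded. They are not: III.e already has them de-identified and given a study ID. How the cell saver treats irrigant is a missing detail that the documents cannot settle, not a contradiction, and it is not pressed here.

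**Conclusion.** The point holds as an unreconciled description of the primary endpoint, together with a blinding statement that Method 2 cannot meet as written. It should be fixed, but it is not a design failure. It assumes that the averaged measurements in III.c are the Method 2 photograph readings, which follows because no other method has two readings.

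Two stronger readings are tempting and unsupported:

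- **Inflated type I error.** If analysts could freely pick the better of two independent EBL values in a single test at 0.05, the error would be 1 − 0.95² = 0.0975. Two measures of the same blood loss are not independent, and the primary label in II.e argues against free choice. The figure does not describe this trial.
- **A biased treatment comparison.** The documents give no direction or size of error for any method, so nothing can be said about which arm would be favoured.

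**What to change.** 1. In III.c, confine the averaging and non-differential statements to Method 2. If Method 2 is in fact intended as primary, change II.e instead. State once, in III.d or III.e, that the chosen source divided by levels fused is the value tested at both the interim and the final analysis.
2. Report the other two methods, which are already to be collected, as pre-specified sensitivity analyses.
3. For Method 2, have the blinded evaluators record only volumes from the study-ID-coded photographs, and let the database or the statistician do the arm-specific irrigation subtraction. If the USBS bag is among those photographed, show images singly so that the number of bags per patient does not reveal the arm.

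The cost is a few lines of wording and a small change in who does the subtraction. Sample size, boundaries and patient care are unaffected.
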